A copy of this amended protocol will be sent to the Institutional Review Board (IRBs)/Independent Ethics Committee (IECs) and Health Authorities.

Protocol summary

Protocol number	CSAF312B12201
Full Title	A 12-week parallel group, randomized, placebo-controlled, double-blinded, multicenter study to evaluate efficacy and safety of 2 concentrations of SAF312 eye drops (5 mg/ml and 15 mg/ml) used twice-dailyin the treatment of post-operative corneal induced chronic pain (CICP) following Photorefractive Keratectomy (PRK) or Laser-assisted in Situ Keratomileusis (LASIK) surgeries.
Brief title	Study of efficacy and safety of SAF312 eye drops in subjects with post-operative corneal induced chronic pain (CICP)
Sponsor and Clinical Phase	Novartis Phase II
Investigation type	Drug
Study type	Interventional
Purpose and rationale	The study is designed to demonstrate the safety and efficacy of two dose concentrations of SAF312 eye drops (5 mg/ml and 15 mg/ml) in subjects with CICP persisting at least for 4 months after refractive or cataract surgery and chronicity confirmed during the observational period. The study will also determine the optimal dose to carry forward for further development.
Primary Objective	To demonstrate the efficacy of at least 1 of 2 concentrations of SAF312 (5 mg/ml or 15 mg/ml) with superiority to placebo in reducing ocular pain severity.
Secondary Objectives	 To evaluate additional efficacy of 2 concentrations of SAF312 vs placebo (e.g., time to pain improvement, quality of life) To demonstrate SAF312 does not induce negative effects to the ocular surface after prolonged TRPV1 inhibition To evaluate the safety of 2 concentrations of SAF312 (5 mg/ml and 15 mg/ml)
Exploratory objectives	 To monitor a subject's behavior regarding use of artificial tear/gel/lubricant and rescue medication To evaluate corneal nerve density and morphology
Study design	This study is a Phase 2 randomized, double-blinded, multi-center, parallel group, placebo-controlled evaluation of the safety and efficacy of SAF312, 5 mg/ml and 15 mg/ml eye drops versus placebo used twice-daily in both eyes for 12 weeks. Eligible subjects will have undergone refractive surgery (i.e., PRK, LASIK, LASEK, RK, or SMILE) or cataract surgery in both eyes with or without refractive enhancement in one or both eyes at least 4 months prior to Screening, and have been suffering from chronic ocular pain as a result of the their surgery. Eligible patients must also demonstrate chronicity of the pain at Baseline Visit as described in inclusion criteria. Overall approximately 150 subjects will be enrolled in the study and randomized to one of 3 study arms in 1:1:1 ratio
Population	The study population will consist of subjects (≥ 18 years old) with persistent ocular surface pain for at least 4 months after refractive or cataract surgery

	(including clear lensectomy). The goal is to randomize a total of approximately
	150 subjects.
Key Inclusion criteria	• Subjects who have undergone refractive surgery (i.e., PRK, LASIK, LASEK, RK, or SMILE) or cataract surgery in both eyes, with or without refractive enhancement in one or both eyes, ≥4 months prior to Screening Visit and experiencing persistent ocular surface pain since the surgery, and have been seen by an ophthalmologist or optometrist at least once with complaint of continued ocular pain since surgery.
	NOTE: The 4 month requirement must be based on the date of the last surgery.
	• Subjects who demonstrate a ≥ 60% reduction in ocular pain within 5 minutes after instillation of a single topical ocular anesthetic drop at Screening Visit.
	At Baseline
	 Subjects with an average pain severity VAS score of ≥ 30 mm based on Daily eDiary for the last 7 days prior to Baseline Visit (Visit 2).
	 Subjects who have reported pain severity >10 mm based on Daily eDiary for > 50% of the days of the observational period (Screening).
Key Exclusion criteria	 Use of nerve growth factor eye drops within 14 days of the Screening Visit Seasonal allergic conjunctivitis, or other acute or seasonal ocular diagnosis that are active at the time of Screening or would be active during the course of the study.
	 Any history of ocular herpes simplex virus or herpes zoster virus infection, or other severe ocular conditions such as graft versus host disease, Stevens- Johnson syndrome or sarcoidosis.
	Presence of any ocular infection (bacterial, viral, or fungal) within 30 days prior to Screening.
	Chronic topical ocular medications (i.e., cyclosporine, lifitegrast) initiated <6 months prior to Screening Visit, or any anticipated change during the study.
	 Use of ocular or nasal corticosteroids within 30 days of Screening Visit. Use of neuromodulatory medications (e.g., gabapentin, pregabalin) or opioid use for non-ocular pain within 30 days of Screening Visit.
	• Chronic medications (both over the counter and prescription) that have not been stable for at least 30 days prior to Screening Visit, or any anticipated change in the chronic medication regimen.
	Subjects requiring hospitalization within 6 months prior to screening for severe psychiatric disorders or major psychiatric illness (e.g., psychosis, schizophrenia, mania, depression).
Study treatment	Subjects will be assigned one of the following 3 treatments - SAF312 5 mg/ml (0.5%), SAF312 15 mg/ml (1.5%) or SAF312 placebo eye drops, administered as one drop in each eye twice-daily for three months
Efficacy assessments	 Pain Severity Visual Analog Scale (VAS) Pain Frequency VAS OPAS questionnaire
Key safety assessments	 Visual Acuity Slit Lamp Examination Intraocular Pressure Dilated Fundus Exam

	-
	Corneal Endothelial Cell Microscopy
Other assessments	 In Vivo Confocal Microscopy Conjunctival Redness Corneal Fluorescein Staining Conjunctival Lissamine Staining Schirmer's Test Pain Characterization Questionnaire
Data analysis	The primary objective of the study is to show that at least one SAF312 arm will improve weekly mean pain severity VAS score in comparison with its placebo by rejecting the null hypothesis below at a significance level α =0.05 (2-sided). Mixed model repeated measure (MMRM) analysis will be used with change from baseline at each week on treatment as response variable, and treatment, week, and baseline score as covariates. Two interaction term (treatment*week and baseline*week) will also be included in the model. The two-sided p value for the least square mean (LSM) difference between the SAF312 and the placebo group at each week will be reported for the difference.
Key words	Eye pain, corneal induced chronic pain (CICP), photorefractive keratectomy (PRK), laser-assisted in situ keratomileusis (LASIK), Laser Assisted Sub-Epithelial Keratectomy (LASEK), Radial Keratotomy (RK), Small Incision Lenticule Extraction (SMILE), Cataract, adults, randomized study, placebo

1 Introduction

1.1 Background

Transient Receptor Potential Vanilloid 1 (TRPV1) receptors belong to the superfamily of TRP Ca²⁺-permeable non-selective cation channels (Clapham et al 2001). These channels are expressed primarily on a subset of somatic and visceral primary afferent sensory neurons (Holzer 2004; Gunthorpe et al 2002; Hayes et al 2000). TRPV1 can be activated by capsaicin, noxious heat, acidic solutions, mechanical distortion, hyperosmolarity and inflammatory mediators such as bradykinin, prostaglandins and nerve growth factor (NGF), which are likely to be released or upregulated by tissue damage or in specific disease conditions (Caterina and Julius 2001; Geppetti and Trevisani 2004). The activation of TRPV1 results in nociceptive stimuli interpreted by the brain as pain. Importantly, chronic peripheral nociceptor activity can further increase the release of the inflammatory mediators which regulate TRPV1 activity, and results in a sensitization of the channel and a lowering of its thresholds for activation causing hyperalgesia and allodynia. Taken together, these findings indicate that TRPV1 is a key integrator of nociceptive and inflammatory response information.

Accumulating data indicates a primary role for TRPV1 receptors in ocular pain (Zhang et al 2007; Yang et al 2013; Mergler et al 2010). Furthermore, the chronic stimulation of corneal and conjunctival nerves in many ocular conditions, creates a cycle of stimulus amplifications due to damage on the ocular surface, inflammation, and constant exposure of inflammatory cytokines in the tears. This is of particular importance in regards to the highly innervated cornea.

SAF312 is a highly selective and potent antagonist of TRPV1. Topical ocular administration of SAF312 in nonclinical studies has resulted in high ocular exposure with relatively low systemic exposure, which could enable ocular pain management while avoiding known systemic side effects associated with TRPV1 antagonism (eg, heat insensitivity, transient hyperthermia, autonomic dysreflexia in patients with spinal cord injury). Plasma exposure of SAF312 after 4-times daily ocular administration of 15 mg/ml (1.5%) eye drops (the highest dose to be used in this study) was very low (Day 8 Cmax (maximum of serum concentration), 0.941 ng/mL and AUC0-24h, 15.1 ng*h/ml) and at least 100-fold and 37-fold lower than corresponding exposure values (Cmax, 93.9 ng/ml and AUCtau, 554 ng*h/ml) after repeated oral dosing of 12.5 mg b.i.d. where tolerability risks were not observed, yet noted at higher oral doses.

Two clinical studies with topical ocular SAF312 eye drops, suspension (eye drops) have been conducted to date. One study was the first in human (FIH) study assessing the safety of SAF312 eye drops, followed by a proof of concept study for acute pain relief after PRK surgery compared to vehicle. The safety of topical ocular SAF312 eye drops has been demonstrated in both studies for all tested dose concentrations of 1.5 mg/ml to 25 mg/ml (0.15% up to 2.5%), no indication of delayed wound healing, and esthesiometry measurements demonstrated no anesthetic effect when compared to tetracaine 0.5% (marketed topical ocular anesthetic as positive control) or vehicle (as negative control). These findings are of importance to provide reassurance that the drug is not simply anesthetizing the ocular surface and leaving the patient at risk due to inhibition of the natural ocular defensive mechanisms or inhibition of corneal epithelial cell migration (e.g., response to injury). Proof of concept for the efficacy of SAF312 eye drops was demonstrated with the study meeting both primary endpoints of a statistically

significant difference in Visual Analogue Scale (VAS) pain severity score at 6 hours post-operatively, and the average of 0-12 hour VAS between SAF312-treated eyes and Vehicle-treated eyes. For detailed information, please refer to the IB.

Although many patients suffer from acute ocular pain due to various causes, the treatment of corneal induced chronic pain remains an unmet need since there are currently no topical ocular treatments available that are safe to be used chronically. CICP may be considered as neuropathic in nature, but is perpetuated by continuous nociceptive stimuli from the peripheral neurons. It is also known that many patients with chronic pain do not necessarily describe their symptom as "pain", and that the description can change from day to day or even within a day. Therefore, the term "pain" is used as an umbrella term which can include other symptoms the patient may describe as painful like burning, stinging, foreign body sensation, stabbing, pressure, grittiness or sandiness.

Due to the fact that CICP is driven by malfunctioning peripheral nerve impulses, treatment with a topical ocular drop could provide significant relief for patients who have a need for chronic treatment.

SAF312 is currently under development as a topical ocular eye drop suspension for the treatment of corneal induced chronic pain (CICP). Chronic ocular pain has been reported with the most common types of elective ocular refractive vision correction surgical procedures, Photorefractive Keratectomy (PRK) and Laser-assisted in situ Keratomileusis (LASIK). It has been reported that approximately 95% of patients experience pain immediately following LASIK or PRK surgery. Many patients have resolution of their pain within 1 month after surgery. However, up to 60% of patients continue to have chronic pain beyond 1 month, and up to 44% after 6 months; in some cases the pain will continue for many years or even permanently (Shtein 2011; Levitt et al 2015; Benatti and Afshari 2016). Therefore, the pain experienced by these patients can be considered as a form of peripheral neuropathy. Similarly chronic pain may occur following other surgeries such as laser-assisted sub epithelial keratectomy (LASEK), radial keratectomy (RK), and small incision lenticule extraction (SMILE) and following cataract surgery.

Patients who experience CICP regardless of the cause, may have concurrent (i.e., coexisting or underlying) ocular conditions which require the use of other ocular medications to treat the concurrent condition(s) as deemed appropriate by the patient's physician. Because SAF312 is intended to perform as an analgesic, current treatments the patient may be using for concurrent ocular conditions will be allowed to continue, and SAF312 eye drops will be administered in addition to those current treatments.

1.2 Purpose

The study is designed to demonstrate the safety and efficacy of two dose concentrations of SAF312 eye drops (5 mg/ml and 15 mg/ml) in subjects with CICP persisting at least for 4 months after refractive or cataract surgery, and chronicity of pain confirmed during the 3 month observation period. The study will also determine the optimal dose to carry forward for further development.

2 Objectives and endpoints

Table 2-1 Objectives and related endpoints

Tak	Table 2-1 Objectives and related endpoints				
Ok	ojective(s)	Endpoint(s)			
Pr	imary objective(s)	ndpoint(s	s) for primary objective(s)		
•	To demonstrate the efficacy of at least 1 of 2 concentrations of SAF312 (5 mg/ml or 15 mg/ml) with superiority to placebo in reducing ocular pain severity		e from baseline to Week 12 in weekly pain severity Visual Analog Scale		
Se	condary objective(s)	indpoint(s	s) for secondary objective(s)		
•	To evaluate additional efficacy of 2 concentrations of SAF312 vs placebo	_	e from baseline to Day 7 and Day 14 ne pain severity VAS		
			e from baseline to Week 12 in pain ncy VAS		
			e from Baseline to Week 12 in Ocular essessment Scale (OPAS) sub-scale of Life		
•	To demonstrate SAF312 does not induce negative effects to the ocular surface after prolonged TRPV1 inhibition	surface conjund	e from baseline to Week 12 in ocular parameters (eg, corneal and ctival staining score, Schirmer score, ctival redness score)		
•	To evaluate the safety of 2 concentrations of SAF312 (0.5 and 1.5%)		rison of adverse events rates n active and placebo		
Ex	ploratory objective(s)	Endpoint(s) for exploratory objective(s)			
•	To monitor a subject's behavior regarding artificial tear/gel/lubricant use		ncy of artificial tear/gel/lubricant use e 12 week treatment period		
•	To monitor a subject's behavior regarding rescue medication use		ncy of rescue medication use over week treatment period		
•	To evaluate corneal nerve density and morphology	corneal	e from Baseline to Week 12 in total nerve fiber length		
		Presen	ce of microneuromas		

Objective(s)	Endpoint(s)	
	Density of corneal dendritiform cells	

2.1 Primary Estimands

The estimand is the precise description of the treatment effect and reflects strategies to address events occurring during trial conduct which could impact the interpretation of the trial results (e.g premature discontinuation of treatment).

The primary clinical question of interest is: What is the effect of SAF312 versus placebo on change from baseline in pain severity after treatment in subjects with CICP, had they not taken rescue or prohibited medications and had they not discontinued treatment?

The justification for the primary estimands is that they will capture the effect of the study drug for the full duration when administered without confounding effects from prohibited medications or rescue medications. Further details can be found in Section 12.

The primary estimands are described by the following attributes:

- 1. Population: subjects with CICP persisting at least 4 months after refractive surgery, and chronicity of pain confirmed during the 3-month observation period. Further details about the population are provided in Section 5.
- 2. Endpoint: change from baseline in ocular pain severity VAS. The score is derived by averaging the seven daily measurements of each week.
- 3. Treatment of interest: the randomized treatment (SAF312 or placebo) with or without treatment for any underlying ocular conditions. Further details about the investigational treatment and control treatment are provided in Section 6.

Handling of remaining intercurrent events (IE):

- 1. Rescue medications: had subjects not taken rescue medication and behaved like other subjects who did not take them (hypothetical strategy)
- 2. Prohibited medications: had subjects not taken prohibited medication and behaved like other subjects who did not take them (hypothetical strategy)
- 3. Treatment discontinuation for any reasons: had patients taken the assigned treatment for the entire study duration and behaved like other subjects who did not discontinue treatment (hypothetical strategy)

The summary measure: difference in variable means between SAF312 and placebo.

[figure not shown]
Supplementary estimands to the primary estimand are defined in Section 12.

2.2 Secondary Estimands

Not applicable.

3 Study design

Figure 3-1 Study Design

This study is a Phase 2 randomized, double-blinded, multi-center, parallel group, placebo-controlled evaluation of the safety and efficacy of SAF312, 5 mg/ml and 15 mg/ml eye drops versus placebo used twice-daily in both eyes for 12 weeks. Eligible subjects will have undergone refractive surgery (i.e., PRK, LASIK, LASEK, RK, or SMILE) in both eyes or cataract surgery in both eyes, with or without refractive enhancement in one or both eyes at least 4 months prior to Screening, and have been suffering from chronic ocular pain as a result of the their surgery. Both eyes do not necessarily need to have undergone surgery on the same day. If the second eye underwent surgery on a different day than the first, eligibility for time since surgery would be based on the date of the most recent surgery. In cases where more than one procedure was performed on an eye (eg, refractive surgery with CICP followed some time later by cataract surgery, or cataract surgery followed some time later by refractive enhancement), the Screening visit must be \geq 4 months after the most recent procedure. Eligible patients must also demonstrate chronicity of the pain as described in inclusion criteria. Overall approximately 150 subjects will be enrolled in the study (i.e. approximately 50 subjects will be enrolled in each treatment arm in 1:1:1 ratio).

The study will consist of a 12 week observation period starting from Screening Visit (Visit 1) until the Baseline/Randomization Visit (Visit 2). Subjects who qualify for randomization will then be asked to attend visits every two weeks for the first 4 weeks, and then monthly for the remainder of the 12 week treatment period. End of Treatment (EOT) will occur at Visit 6 when the subject receives the last study treatment. End of Study (EOS) will occur 4 days after EOT.

Potential participants will be required to provide written informed consent prior to any study-specific Screening procedures being performed. Once informed consent is obtained subjects will be evaluated for eligibility based on the inclusion and exclusion criteria (Section 5). Final eligibility will be based on an assessment of the subject's pain severity VAS prior to randomization, as well as their response to a single drop of topical ocular anesthetic (eg, tetracaine, proparacaine eye drops per clinical practice). Response to anesthetic is defined as a ≥ 60% reduction in ocular pain within 5 minutes after instillation of the anesthetic drop. The use of the anesthetic test is necessary for the selection of subjects with a primarily peripheral neuropathic type pain (i.e., primarily resulting from stimulation of the peripheral nerves) versus a purely central neuropathic pain. Subjects with a primarily central neuropathic pain are unlikely to experience significant improvement with a topical ocular treatment targeting the peripheral nerves. Subjects who meet eligibility criteria at Visit 2, will be randomized to one of the three treatment groups (SAF312 5 mg/ml, SAF312 15 mg/ml, placebo) in a 1:1:1 ratio. Subjects will visit the study site for assessments as outlined in the visit assessment schedule (see Table 8-1).

All subjects will be allowed to continue their current treatment regimen for any underlying or unrelated ocular condition if applicable (eg, treatment for glaucoma, dry eye) as long as eligibility criteria are met. No new treatments can be initiated once the subject has begun participation in the study unless additional treatments are needed for proper management of an adverse event. Whenever topical ocular eye drops other than the investigational medicinal product (IMP) are administered, the subject should first dose with their concomitant medication(s) and wait approximately 10 minutes prior to instillation of the assigned IMP.

4 Rationale

4.1 Rationale for study design

This study will evaluate the safety and efficacy of two concentrations of SAF312 twice daily for 12 weeks in the treatment of CICP following refractive or cataract surgery. The aim is to evaluate the treatment effect of SAF312 compared to placebo, and to determine the appropriate concentration to carry forward for further development.

The active and placebo IMPs will be presented in identical packaging to ensure no bias to the study results due to knowledge of the treatment assignment. Due to the difference in appearance of SAF312 eye drops vs placebo eye drops (milky white vs clear, respectively), sites will be required to have an unblinded staff member to manage drug dispensation, drug accountability, as well as collection of adverse events or subject reports of product comments/complaints. All other site staff and Sponsor staff will be blinded to treatment assignments. To ensure masking of subjects to their treatment assignment, no subject will receive both placebo and active treatment so no change in appearance of the test article will be noticeable by a particular subject. Subjects may be informed that their study treatment may appear cloudy or white, but must not be informed about the specific identity of the treatments based on differences in appearance.

A 12-week observation period prior to randomization is included as a method to confirm the chronicity of their ocular pain, observe trends in the subject's pain occurrences (
), and to observe behaviors with artificial tears and rescue medications prior to receiving randomized treatment. This observation period confirms the selection of

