6.4 Treatment blinding

Subjects, investigator staff, persons performing the assessments, study monitors and Clinical Trial Team (CTT) will remain blind to the identity of the treatment from the time of randomization until database lock, using the following methods: (1) Randomization data are kept strictly confidential until the time of unblinding and will not be accessible by anyone else involved in the study with the following exceptions: unblinded site personnel will be required for initial dose administration, and discussions with subjects that may contain unblinding information (2) the identity of the treatments will be concealed by the use of study treatment that are all identical in packaging, labeling, and schedule of administration.

Unblinding of the investigator may occur in the case of subject emergencies and at the conclusion of the study.

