⁷ To be conducted at selected sites only

⁸ Study medication is only dispensed after the subject is randomized

⁹ Review subject daily eDiary entry compliance and subject reported outcome of Pain Severity VAS, Pain Frequency, Frequency of Artificial Tear use and rescue medication use. If pain rescue medication were reported in eDiary, request further detailed medication information and make entry into eCRF concomitant medication page.

Table 8-2 Proposed in-office Assessment Sequence

Visit 1 (Screening)	Visit 2 (Baseline/ Randomization)	Visits 3 / 4 / 5	Visit 6 (EOT)	
ICF / Demographics / MH / Incl + Excl	Con meds / AE / MH / Incl + Excl	Con meds / AE	Con meds / AE	
Concomitant medications / adverse events	Pregnancy test	OPAS questionnaire	Pregnancy test	
Placebo response mitigation training video ¹	Confirm eligibility on pain severity VAS		eDiary compliance check	
Dispense eDiary	eDiary compliance check	ary compliance check Slit-lamp exam		
Pain severity and frequency VAS	OPAS questionnaire	Conjunctival redness		
Use of artificial tears / rescue medications		Corneal fluorescein staining	Visual acuity	
Pain Characterization questionnaire	Visual acuity	Lissamine conjunctival staining	Slit-lamp exam	
OPAS questionnaire	Slit-lamp exam	Schirmer test	Conjunctival redness	
	Conjunctival redness	eDiary compliance check	Corneal fluorescein staining	
Visual acuity	Corneal fluorescein staining	Contact IRT	Lissamine conjunctival staining	
Slit-lamp exam	Lissamine conjunctival staining	Collect/dispense IMP	Schirmer test	
Conjunctival redness	Schirmer test	eDiary reminders	IOP	
Corneal fluorescein staining	IOP		Dilated fundus exam	
Lissamine conjunctival staining	Dilated fundus exam		Specular Microscopy / *Confocal microscopy	
Schirmer test	Specular Microscopy / Confocal microscopy ²		Collect meds / devices	
Anesthetic test	Contact IRT		Contact IRT	
Contact IRT	Randomize/dispense IMP			
	Dose in clinic (unblinded site personnel only)			
eDiary reminders	eDiary reminders			
	Placebo response mitigation training video ³			

NOTE:

¹ Includes Pain Assessment Knowledge Check

² Confocal microscopy is performed only at select sites after specular microscopy

³ Pain Assessment Knowledge Check can be performed optionally at Visit 2, but should be performed if not completed previously

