10.1 Definition of adverse events and reporting requirements

10.1.1 Adverse events

An AE is any untoward medical occurrence (e.g. any unfavorable and unintended sign [including abnormal laboratory findings], symptom or disease) in a subject or clinical investigation subject after providing written informed consent for participation in the study. Therefore, an AE may or may not be temporally or causally associated with the use of a medicinal (investigational) product.

The investigator has the responsibility for managing the safety of individual subject and identifying adverse events.

Novartis qualified medical personnel will be readily available to advise on trial related medical questions or problems.

The occurrence of adverse events must be sought by non-directive questioning of the subject at each visit during the study. Adverse events also may be detected when they are volunteered by the subject during or between visits or through physical examination findings, laboratory test findings, or other assessments.

Adverse events must be recorded under the signs, symptoms, or diagnosis associated with them, accompanied by the following information (as far as possible) (if the event is serious refer to Section 10.1.2):

1. The severity grade

mild: usually transient in nature and generally not interfering with normal activities moderate: sufficiently discomforting to interfere with normal activities

severe: prevents normal activities

- 2. Its relationship to the study treatment. If the event is due to lack of efficacy or progression of underlying illness (i.e. progression of the study indication) the assessment of causality will usually be 'Not suspected.' The rationale for this guidance is that the symptoms of a lack of efficacy or progression of underlying illness are not caused by the trial drug, they happen in spite of its administration and/or both lack of efficacy and progression of underlying disease can only be evaluated meaningfully by an analysis of cohorts, not on a single subject
- 3. Its duration (start and end dates or ongoing) and the outcome must be reported
- 4. Whether it constitutes a SAE (see Section 10.1.2 for definition of SAE) and which seriousness criteria have been met
- 5. Action taken with study treatment

All adverse events must be treated appropriately. Treatment may include one or more of the following:

- Dose not changed
- Dose Reduced/increased

- Drug interrupted/permanently discontinued
- 6. its outcome

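### Protocol 4.1 gives adverse event collection to the unblinded site member, which conflicts with 6.4, 10.1.1 and Table 8-2 and can bias the active-versus-placebo comparison of event rates

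*Protocol*

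**What the plan says.** Protocol 4.1 gives the reason for an unblinded role: "Due to the difference in appearance of SAF312 eye drops vs placebo eye drops (milky white vs clear, respectively"). For that reason "sites will be required to have an unblinded staff member to manage drug dispensation, drug accountability, as well as collection of adverse events". The sentence goes on to add, joined by an or, subject reports of product comments or complaints. It is followed by: "All other site staff and Sponsor staff will be blinded to treatment assignments".

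Section 6.4 sets the general rule: "Subjects, investigator staff, persons performing the assessments, study monitors and Clinical Trial Team (CTT) will remain blind to the identity of the treatment". Its exception reads: "unblinded site personnel will be required for initial dose administration, and discussions with subjects that may contain unblinding information". Adverse event collection is not named there.

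Section 10.1.1 makes the investigator responsible for identifying adverse events and says how they are to be found: "The occurrence of adverse events must be sought by non-directive questioning of the subject at each visit during the study". It does not say whether the questioner is blinded. In Table 8-2 one step is restricted, "Dose in clinic (unblinded site personnel only"), and the adverse event entries carry no such mark.

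Table 2-1 lists the comparison of adverse event rates between active and placebo as a secondary endpoint. Protocol 12.5.1 and SAP 2.8.1 summarise events by treatment, by maximum severity and by relation to treatment.

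**The concern.** Adverse events here come from an open question put to the subject, followed by a judgement on what to write down, how severe it is and whether it is related. Each step can shift with what the questioner knows. What the drop's appearance reveals, active or placebo, is exactly the contrast in the secondary endpoint. A collector with that knowledge might probe or record more in the active arms, or discount what active subjects say, so the bias could run either way.

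The inconsistency adds a second problem. One site could follow 4.1 and another 6.4 with 10.1.1, both in good faith, and the method of collection would then differ between sites without any record of it. Neither document provides for blinded review of collected events, and Protocol 10.2 (additional safety monitoring) is marked not applicable.

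**Working it through.** **Who collects events, place by place**

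| Place | Unblinded role | Adverse events |
|---|---|---|
| Protocol 4.1 | Dispensing, accountability, event collection, product comments | Given to the unblinded member |
| Protocol 6.1.1, 6.7 | First dose in clinic, questions on product identity, instruction and dispensing | Not mentioned |
| Protocol 6.4 | First dose, discussions that may unblind | Not named; investigator staff and assessors blind |
| Protocol Table 8-2 | In-clinic dose only | Listed at each visit, unmarked |
| Protocol 9.3 | None stated | Telephone question 4 days after end of treatment, caller's status not stated |
| Protocol 10.1.1 | None stated | Investigator, blind under 6.4, identifies events; questioner not stated |

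Only 4.1 names a collector, and it names the unblinded one. The other entries point to blinded collection, but none says so outright.

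SAP 2.1.1.1 describes all strengths and placebo as identical in appearance. If that meant the drops themselves, the collector would learn nothing and the concern would fall away. Read with its reference to the droptainers it can mean the container only, and Protocol 4.1 is explicit that the drops differ. The two statements should be reconciled as well.

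**Size**

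The plan states no adverse event rate or precision, so there is no figure to reproduce. The following is illustration on assumed rates.

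*One active arm against placebo.* Inputs: 50 per arm (Protocol 12.8.1); assumed true rate 20% in both arms; assumed relative over-recording r in the active arm of 10%, 25% or 50%.

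- False difference = 0.20 × r.
- 95% half-width = 1.96 × √[p₁(1−p₁)/50 + p₀(1−p₀)/50], with p₀ = 0.20 and p₁ = 0.20 × (1 + r).

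| r | Recorded active rate | False difference | Half-width | Ratio |
|---|---|---|---|---|
| 10% | 22% | 2 points | 16.0 points | 0.13 |
| 25% | 25% | 5 points | 16.3 points | 0.31 |
| 50% | 30% | 10 points | 16.9 points | 0.59 |

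With both arms at 20% the half-width is 1.96 × √(2 × 0.2 × 0.8/50) = 15.7 points. Under-recording in the active arm by the same fractions gives −2, −5 and −10 points.

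*Both active arms pooled against placebo (100 against 50).* Here placebo events are assumed to be recorded at 90% or 75% of the active recording rate.

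| True rate | False difference (90% to 75%) | Standard error |
|---|---|---|
| 10% | 1.0 to 2.5 points | about 5 points |
| 20% | 2 to 5 points | 6 to 7 points |
| 40% | 4 to 10 points | about 8 points |

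If only a share f of subjects attend sites that follow 4.1, the average false difference is f times these values. The documents do not fix f, so it ranges from 0 to 1. More subjects do not help: at the permitted 60 per arm the half-width falls to 1.96 × √(2 × 0.2 × 0.8/60) = 14.3 points, while the false difference stays the same.

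**The case against.** The best defence is that 4.1 is a rationale section and its sentence is about drop appearance. Read with the product comments that follow and with the exception in 6.4, the task may mean only receiving reports that could reveal what the drops look like. Sections 6.4 and 10.1.1 and Table 8-2, which govern conduct, point to blinded identification. This stands in part. The narrow reading is possible, so it is not established that the endpoint was collected unblinded. But 4.1 as written also permits the broad reading, and no passage excludes it.

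A reader might infer three stronger things that the documents do not support.

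- *That the unblinded member decides what counts as an event.* Section 4.1 speaks of collection; 10.1.1 gives identification to the investigator.
- *That dose choice is compromised.* Appearance is said to separate active from placebo. Nothing says it separates 5 from 15 mg/ml, so no bias between the two doses is shown.
- *That efficacy is affected, because adverse events are a ground for stopping treatment and the primary estimand drops later data.* The primary endpoint is a diary score completed by the subject. Stopping is initiated by the subject or the investigator, both blind under 6.4. No mechanism is shown by which the collector would change either.

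The defence also notes a real cost. If subjects discuss all events with blinded staff, some may describe the drops to the investigator, who also grades redness and staining, themselves secondary endpoints. That stands as a small trade-off. SAP deviation code OTH09 records such a breach but does not undo it, since those subjects remain in all analysis sets.

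**Conclusion.** The inconsistency is real and in current text. Section 4.1 assigns adverse event collection to someone who can tell active from placebo, while 6.4, 10.1.1 and Table 8-2 point to blinded collection without stating it. What is at risk is the active-versus-placebo comparison of event rates. That comparison is descriptive, so the harm is biased rates and a possible difference in method between sites, not an inflated type I error.

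The direction and size of any bias are unknown. The 2 to 10 points for a single active arm rest wholly on an assumed 20% true rate, assumed recording differences and every site following 4.1. Even there the bias stays below the half-width of the interval. It is still worth removing, because it is avoidable, would not be visible in the data and does not shrink with sample size.

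**What to change.** Reconcile Protocol 4.1, 6.4, 10.1.1 and Table 8-2.

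- In 4.1, remove general adverse event collection from the unblinded role.
- In 6.4 and 10.1.1, state that blinded site staff elicit, record, grade and attribute adverse events by non-directive questioning. Mark Table 8-2 to match, and cover the end-of-study telephone contact.
- Limit the unblinded member to dispensing, the first dose, and comments or complaints about product appearance. Any symptom mentioned in such a report is passed to blinded staff without the appearance information.
- Tell subjects at Visit 2 not to describe the drops to blinded staff.
- Clarify in SAP 2.1.1.1 whether identical appearance refers to the container or to the drops.

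If events were already collected unblinded, record by site who collected them and state the limitation in the study report.

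The cost is protocol wording and a line of site training, with no extra staff or procedure. The remaining downside is an occasional description of the drops to a blinded assessor, logged under OTH09.
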